6.1 What are the primary inclusion criteria?

Enrolled and active first-year graduate students at Wichita State University,
Participants between the ages of 20 and 35.

6.2 What are the primary exclusion criteria?

Students with diagnosed dog allergies; students with a fear of dogs; students diagnosed with mental health disorders; students with ongoing mental health treatment including (con't...)

7. Is Compensation Offered? Yes No If "Yes", describe amount, type (gift card, greenphire, etc) and when:

8. Describe the recruitment process, including any advertisements (flyers, emails, phone scripts, Strategic Communications Ads, etc.) to be used for this study. Include the flyer and text of the ads, emails, scripts as applicable in a separate document.

Participants will be recruited via an in-person presentation and explanation of the study by the research team.

Participants will be given the opportunity to sign up and navigate inclusion/exclusion criteria via a Qualtrics survey via a link sent through email from the PI.

https://wichitastate.co1.qualtrics.com/jfe/preview/previewId/fe71f770-cbe3-414e-9174-865c7a4135db/SV_e9UIEaLk6Jdx0wu?Q_CHL=preview&Q_SurveyVersionID=current

Risks/Benefit Information

1. Potential Risk Exposure: Physical (cognitive or motor) Psychological Economical Legal Social

2. Describe the nature and degree of the risks. (Do not say N/A - It cannot be assumed that there are no risks). Be sure all items listed are described in the informed consent document.

1. Minor physical risk from the human-animal interaction,
2. Minor physical risk from the salivatory cortisol test,
3. Minor physical risk for pain due to the pain pressure threshold testing/algometer.

3. Describe how risks and discomforts (physical, psychological, or social) will be minimized:

1. Risks due to animal interaction are minimized by having the animals trainer present, the animal having canine good citizen certification, and currently working through progression towards therapy dog certification.

2 & 3. Physical risks will be limited by training researchers and educating participants on research parameters.

2. All researchers will be properly trained how to obtain a salivatory cortisol test.
3. All researchers will be properly trained on the use of the pain pressure threshold algometer.

4. Please describe the benefits of the research to human subjects, if any, and of the benefits to human or scientific knowledge:

The anticipated findings may demonstrate the beneficial effects of HAI on student well-being, potentially encouraging universities to offer such opportunities regularly throughout the academic year. Beyond reducing stress, these interactions may enrich the overall student experience, foster positive relationships with animals, and promote the adoption of healthy coping strategies for managing academic-related stress. Further, for the animals involved, it facilitates socialization and play.

Ultimately, the translation of these findings could benefit students not only at Wichita State University but also across other Kansas universities and community colleges. The results are

Confidentiality

1. How will you safeguard data that includes identifying or potentially identifying information (e.g. coding)? N/A

All data containing participant information will be password protected and only available to the PI/co-investigators. All data will be released only in aggregate form. Participants will be assigned an identification number. The co-investigators involved in data analysis will only have access to the scores and measurements associated with the assigned identification numbers.

2. When will identifiers be separated or removed from the data? N/A

During the first session. During all subsequent sessions, the participants will be referred to via their unique identification number.

3. Where and how will you store the data?

All paper data collection will be kept in a locked file cabinet in the principal investigator's locked office; electronic data will be in a password protected, WSU-owned laptop.

4. How long do you plan to retain the data? *Research Records must be maintained for a minimum of 5 years after completion of the study. This is based on the longest required retention period under the various applicable federal regulations.*

5 years

5. Describe how you will dispose of the data (e.g. erasing tapes, shredding data)?

Paper data will be shredded after 5 years and computer data will be deleted with the assistance of WSU's Information Technology department.

Informed Consent

1. What type of informed consent will be obtained (may select more than one):

- Written consent with signatures obtained
- Consent document given but no signature obtained
- N/A - explain:

2. Specify the consent forms included with this submission: Adult Parent Child Assent Foreign Language
Other:

3. Are you requesting a waiver of consent or assent? Yes No *If yes, explain how the research meets the federal criteria (45 CFR 46.116(d)) for waiving the informed consent requirement:*

- a) The research involves no more than minimal risk to subjects. Yes No
- b) The research could not practicably be carried out without the requested waiver or alteration. Yes No
- c) If the research involves using identifiable private information or identifiable biospecimens, the research could not practicably be carried out without using such information or biospecimens in an identifiable format Yes No
- d) The waiver will not adversely affect the rights and welfare of the subjects. Yes No
- e) Whenever appropriate the subjects or legally authorized representatives will be provided with additional pertinent information after participation. Yes No

4. Describe the informed consent **process**. How and by whom will initial contact with potential subjects take place? Where and when will the consent interview take place?

Or mark N/A

After the participants have met inclusion criteria, verbally consented to participate, met the requirements to be a participant, and signed the consent form they will be sent an acceptance email, from the PI, with the study start date, instructions, contact information of one of the researchers for questions and a copy of the consent form for their records. The participants will have the ability to ask any clarifying questions via email before the study starts and throughout the entirety of the study.

If you are requesting an **Exempt** review please check the categories of exemption for which you are applying. You may check more than one box. See Category descriptions below. Note – these descriptions are truncated. The full text can be found under 45 CFR 46.104

N/A if not Exempt

Category 1. Research conducted in established or commonly accepted educational settings that specifically involves normal educational practices that are not likely to adversely impact students' opportunity to learn required educational content or the assessment of educators who provide instruction, involving normal educational practices. This includes most research on regular and special education instructional strategies and research on the effectiveness of or the comparison among instructional techniques, curricula or classroom management methods.

Category 2. Research that only includes interactions involving educational tests (cognitive, diagnostic, aptitude, achievement), survey procedures, interview procedures, or observation of public behavior (including visual or auditory recording) if at least one of the following criteria is met:

- a. The information obtained is recorded by the investigator in such a manner that the identity of the human subjects cannot readily be ascertained, directly or through identifiers linked to the subjects;
- b. Any disclosure of the human subjects' responses outside the research would not reasonably place the subjects at risk of criminal or civil liability or be damaging to the subjects' financial standing, employability, educational advancement, or reputation; **or**
- c. The information obtained is recorded by the investigator in such a manner that the identity of the human subjects can readily be ascertained, directly or through identifiers linked to the subjects, and an IRB conducts a limited IRB review to make the determination.

PLEASE NOTE: the only research activities involving children that may fall under this exemption are those involving educational tests or observation of public behavior where the investigators do not participate in the activity being observed.

Category 3(i). Research involving benign behavioral interventions in conjunction with the collection of information from an **adult** subject through verbal or written responses (including data entry) or audiovisual recording if the subject prospectively agrees to the intervention and information collection and at least one of the following criteria is met:

- a. The information obtained is recorded by the investigator in such a manner that the identity of the human subjects cannot readily be ascertained, directly or through identifiers linked to the subjects; **or**
- b. Any disclosure of the human subjects' responses outside the research would not reasonably place the subjects at risk of criminal or civil liability or be damaging to the subjects' financial standing, employability, educational advancement, or reputation; **or**
- c. The information obtained is recorded by the investigator in such a manner that the identity of the human subjects can readily be ascertained, directly or through identifiers linked to the subjects, and an IRB conducts a limited IRB review to make the determination.

(ii) For the purpose of this provision, benign behavioral interventions are brief in duration, harmless, painless, not physically invasive, not likely to have a significant adverse lasting impact on the subjects, and the investigator has no reason to think the subjects will find the interventions offensive or embarrassing. Provided all such criteria are met, examples of such benign behavioral interventions would include having the subjects play an online game, having them solve puzzles under various noise conditions, or having them decide how to allocate a nominal amount of received cash between themselves and someone else.

(iii) If the research involves deceiving the subjects regarding the nature or purposes of the research, this exemption is not applicable unless the subject authorizes the deception through a **prospective agreement** to participate in research in circumstances in which the subject is informed that he or she will be unaware of or misled regarding the nature or purposes of the research.

Please Note: research activities involving children do not qualify under this exemption

Category 4. Secondary research for which consent is not required: Secondary research uses of identifiable private information or identifiable biospecimens, if at least one of the following criteria is met:

- a. The identifiable private information or identifiable biospecimens are publicly available; **or**
- b. Information, which may include information about biospecimens, is recorded by the investigator in such a manner that the identity of the human subjects cannot readily be ascertained directly or through identifiers linked to the subjects, the investigator does not contact the subjects, and the investigator will not re-identify subjects; **or**
- c. The research involves only information collection and analysis involving the investigator's use of identifiable health information when that use is regulated by HIPAA "health care operations" or "research" or for "public health activities and purposes"; **or**
- d. The research is conducted by, or on behalf of, a Federal department or agency using government generated or government-collected information obtained for nonresearch activities, if the research generates identifiable private information that is or will be maintained on information technology that is subject to and in compliance with specified federal privacy laws.

Category 5. Research and demonstration projects that are conducted or supported by a Federal department or agency, or otherwise subject to the approval of department or agency heads, and that are designed to study, evaluate, improve, or otherwise examine public benefit or service programs. **Note:** these must be posted on a Federal Web site.

Category 6. Taste and food quality evaluation and consumer acceptance studies

Describe how the proposed research meets the criteria for **exemption**. Reference the exemption category or categories (above and on page 7) and the category's corresponding requirements.

If you are requesting an **Expedited** review please check the categories for which you are applying. See category descriptions below. You may check more than one box.

N/A if not Expedited review

Category 1. Clinical studies of drugs and medical devices only when condition (a) or (b) is met. a. Research on drugs for which an investigational new drug application (21 CFR Part 312) is not required. (Note: Research on marketed drugs that significantly increases the risks or decreases the acceptability of the risks associated with the use of the product is not eligible for expedited review.) b. Research on medical devices for which (i) an investigational device exemption application (21 CFR Part 812) is not required; or (ii) the medical device is cleared/approved for marketing and the medical device is being used in accordance with its cleared/approved labeling.

Category 2. Collection of blood samples by finger stick, heel stick, ear stick, or venipuncture as follows: a. from healthy, nonpregnant adults who weigh at least 110 pounds. For these subjects, the amounts drawn may not exceed 550 ml in an 8 week period and collection may not occur more frequently than 2 times per week; or b. from other adults and children, considering the age, weight, and health of the subjects, the collection procedure, the amount of blood to be collected, and the frequency with which it will be collected. For these subjects, the amount drawn may not exceed the lesser of 50 ml or 3 ml per kg in an 8 week period and collection may not occur more frequently than 2 times per week.

Category 3. Prospective collection of biological specimens for research purposes by noninvasive means. Examples: (a) hair and nail clippings in a nondisfiguring manner; (b) deciduous teeth at time of exfoliation or if routine patient care indicates a need for extraction; (c) permanent teeth if routine patient care indicates a need for extraction; (d) excreta and external secretions (including sweat); (e) uncannulated saliva collected either in an unstimulated fashion or stimulated by chewing gumbase or wax or by applying a dilute citric solution to the tongue; (f) placenta removed at delivery; (g) amniotic fluid obtained at the time of rupture of the membrane prior to or during labor; (h) supra- and subgingival dental plaque and calculus, provided the collection procedure is not more invasive than routine prophylactic scaling of the teeth and the process is accomplished in accordance with accepted prophylactic techniques; (i) mucosal and skin cells collected by buccal scraping or swab, skin swab, or mouth washings; (j) sputum collected after saline mist nebulization.

Category 4. Collection of data through noninvasive procedures (not involving general anesthesia or sedation) routinely employed in clinical practice, excluding procedures involving x-rays or microwaves. Where medical devices are employed, they must be cleared/approved for marketing. (Studies intended to evaluate the safety and effectiveness of the medical device are not generally eligible for expedited review, including studies of cleared medical devices for new indications.) Examples: (a) physical sensors that are applied either to the surface of the body or at a distance and do not involve input of significant amounts of energy into the subject or an invasion of the subject's privacy; (b) weighing or testing sensory acuity; (c) magnetic resonance imaging; (d) electrocardiography, electroencephalography, thermography, detection of naturally occurring radioactivity, electroretinography, ultrasound, diagnostic infrared imaging, doppler blood flow, and echocardiography; (e) moderate exercise, muscular strength testing, body composition assessment, and flexibility testing where appropriate given the age, weight, and health of the individual.

Category 5. Research involving materials (data, documents, records, or specimens) that have been collected, or will be collected solely for nonresearch purposes (such as medical treatment or diagnosis). (NOTE: Some research in this category may be exempt from the HHS regulations for the protection of human subjects. 45 CFR 46.101(b)(4). This listing refers only to research that is not exempt.)

Category 6. Collection of data from voice, video, digital, or image recordings made for research purposes.

Category 7. Research on individual or group characteristics or behavior (including, but not limited to, research on perception, cognition, motivation, identity, language, communication, cultural beliefs or practices, and social behavior) or research employing survey, interview, oral history, focus group, program evaluation, human factors evaluation, or quality assurance methodologies. (NOTE: Some research in this category may be exempt from the HHS regulations for the protection of human subjects. 45 CFR 46.101(b)(2) and (b)(3). This listing refers only to research that is not exempt.)

Describe how the proposed research meets the criteria for **expedited** review. Reference the category or categories (on page 8) and the category's corresponding requirements.

#3 - The participants will participate in a buccal cheek swab to obtain salivatory cortisol swabs.

#4 - The participants will have pain pressure thresholds measured using a noninvasive digital pressure algometer on the skin. Participants will also have their blood pressure and heart rate measured via automated blood pressure machines and fingertip oxygen saturation monitors.

#7 - The participants will be asked to complete the Generalized Anxiety Disorder-7 assessment and the Academic Anxiety Scale.

Principal Investigator's Assurance

I certify that the information provided in this application is complete and correct to the best of my ability and knowledge.

I understand that as Principal Investigator, I have ultimate responsibility for the conduct of the study, the ethical performance of the project, the protection of the rights and welfare of human subjects, and strict adherence to any stipulations imposed by the IRB. I accept responsibility to ensure that all study personnel are adequately trained for their role and have read this application.

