7.1c. Will the WSU PI oversee or coordinate the research being conducted at non-WSU sites? Yes No

If yes, Describe the PI's oversight plans, including how the PI will ensure adherence to the study protocol, obtain informed consent, secure and maintain IRB approval at the other sites, monitor adverse events or other unanticipated problems, and ensure general coordination of study conduct.

8. Please summarize the purpose of the proposed research using non-technical language that can be readily understood by someone outside the discipline:

The purpose of the study is to evaluate the effects of human-animal interaction on physiological and psychological markers in graduate students.

Graduate students face significant anxiety due to demanding coursework, long hours of studying, intense academic challenges, and the pressure to excel. Chronic stress in this population can contribute to elevated anxiety levels and measurable physiological changes, such as increased heart rate and blood pressure.

Human-animal interaction (HAI) and its effect on student stress, test anxiety, and physiological markers have been studied on college campuses, largely focusing on undergraduate students. However, research investigating the impact of HAI on graduate student stress, test anxiety, and physiological markers in high-stakes programs is limited. This study will evaluate the effectiveness of repeated HAI on graduate students' physiological markers and anxiety. The results of this study will assist participants, students outside this study, and the program administrators to appreciate the immense value of a full-time therapy dog on campus facilitating the human-animal bond in higher education.

9. Describe each procedure step-by-step, including the frequency, duration, and location of each procedure. A numbered or bulleted list of steps is helpful. *Submit a separate Word document if additional space is needed.*

Research Study:

*Location at [name], specific rooms TBD,

*Completed in the Fall 2025 semester,

*Frequency 1 time per week for 4 weeks,

*https://wichitastate.co1.qualtrics.com/jfe/preview/previewId/fe71f770-cbe3-414e-9174-865c7a4135db/SV_e9UIEaLk6Jdx0wu?Q_CHL=preview&Q_SurveyVersionID=current

Interventions:

Experimental: Human-animal interaction (HAI) - 15 minutes with therapy dog in training in groups of 2-3 participants, spending time doing what the participant wants to do (e.g., sitting quietly with the dog or playing with toys),

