...counseling or medications; students with known history of cardiac pathology and/or on cardiac medications.

List of included documentation:

- Co-investigator documentation
- Consent form
- Kansas Innovation Fund grant application
- Qualtrics email and Facebook announcement
- Non-acceptance email
- Generalized Anxiety Disorder (GAD-7)
- Academic Anxiety Scale (AAS)
- C-Barq questionnaire for therapy dog in training
- Algometer manual
- Algometer picture
- VitalTrack blood pressure cuff and pulse oximeter
- General Health Education (control group) documents:
 - 20 Benefits of Walking 30
 - How to deal with stress and anxiety
 - Sleep Hygiene
 - StressLess

GAD-7 Anxiety

Over the last two weeks , how often have you been bothered by the following problems?	Not at all	Several days	More than half the days	Nearly every day
1. Feeling nervous, anxious, or on edge	0	1	2	3
2. Not being able to stop or control worrying	0	1	2	3
3. Worrying too much about different things	0	1	2	3
4. Trouble relaxing	0	1	2	3
5. Being so restless that it is hard to sit still	0	1	2	3
6. Becoming easily annoyed or irritable	0	1	2	3
7. Feeling afraid, as if something awful might happen	0	1	2	3

Column totals _____ + _____ + _____ + _____ =

Total score _____

If you checked any problems, how difficult have they made it for you to do your work, take care of things at home, or get along with other people?

Not difficult at all

Somewhat difficult

Very difficult

Extremely difficult

Source: Primary Care Evaluation of Mental Disorders Patient Health Questionnaire (PRIME-MD-PHQ). The PHQ was developed by Drs. Robert L. Spitzer, Janet B.W. Williams, Kurt Kroenke, and colleagues. For research information, contact [name] at [contact]. PRIME-MD® is a trademark of Pfizer Inc. Copyright© 1999 Pfizer Inc. All rights reserved. Reproduced with permission

Scoring GAD-7 Anxiety Severity

This is calculated by assigning scores of 0, 1, 2, and 3 to the response categories, respectively, of "not at all," "several days," "more than half the days," and "nearly every day." GAD-7 total score for the seven items ranges from 0 to 21.

0–4: minimal anxiety

5–9: mild anxiety

10–14: moderate anxiety

15–21: severe anxiety

Academic Anxiety Scale

Please complete the following items using the four-point scale below.

1 = Not at all typical of me

2 = Somewhat typical of me

3 = Quite typical of me

4 = Very typical of me

1	I often worry that my best is not as good as expected in school.	1	2	3	4

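### The allergy exclusion reaches only diagnosed dog allergy, so as written it admits a student who knows they react to dogs but was never diagnosed

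*Protocol*

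**What the plan says.** The exclusion list in Subject Selection 6.2 opens with "Students with diagnosed dog allergies; students with a fear of dogs" and then turns to mental health. Its continuation in the supplement finishes the mental-health item and adds "students with known history of cardiac pathology and/or on cardiac medications". Neither part says anything further about allergy. The inclusion criteria in 6.1 are first-year graduate enrolment and an age range.

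On screening, the recruitment item (Subject Selection, item 8) says "Participants will be given the opportunity to sign up and navigate inclusion/exclusion criteria via a Qualtrics survey". The survey itself appears only as a link.

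On exposure, Project Information item 9 describes the experimental condition as "15 minutes with therapy dog in training in groups of 2-3 participants", with the activity left to the participant, and gives the schedule as "Frequency 1 time per week for 4 weeks".

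On risk, Risks/Benefit Information item 2 lists a minor physical risk from interacting with the dog and does not mention allergy. Item 3 says "Risks due to animal interaction are minimized by having the animals trainer present, the animal having canine good citizen certification", and adds that the dog is progressing towards therapy certification.

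**The concern.** By excluding dog allergy at all, the investigators accept that an allergic student should not be put with the dog. The word *diagnosed* then makes that protection depend on whether the student has ever been given a diagnosis, not on whether the student reacts. A student with a known but undiagnosed reaction could answer a question worded like 6.2 honestly and be accepted.

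What is at stake is an avoidable risk to a volunteer. The investigators evidently meant to exclude that risk, and the student can usually report it unaided. The wording matters more because no other safeguard visible in the protocol deals with allergy.

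**Working it through.** The protocol gives no figure to reproduce here. The check is to take one hypothetical applicant, aware of reacting to dogs but never diagnosed, through each relevant part of the protocol.

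| Place in the protocol | What it tests or controls | Does it stop this applicant? |
|---|---|---|
| Inclusion, 6.1 | Enrolment and age | No |
| Exclusion, 6.2, allergy item | A diagnosis of dog allergy | No, there is no diagnosis |
| Exclusion, 6.2, fear item | Fear of dogs | No, a different condition |
| Exclusion, 6.2 and its continuation, other items | Mental-health diagnosis or treatment; cardiac history or medication | No, unrelated |
| Qualtrics sign-up | The criteria, self-navigated | Not if it follows 6.2; items not shown |
| Risks/Benefit, item 3 | Trainer present; dog's certification | No, these concern the dog's behaviour |

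On the criteria as written, the applicant is eligible.

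**Comparison with neighbouring criteria.** Fear of dogs needs no diagnosis, and the cardiac item asks for a known history or medication. The mental-health item does use *diagnosed*, but it is paired with a second route to exclusion, ongoing treatment by counseling or medication. The allergy item has no second route.

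**Exposure if assigned to the dog arm.** Inputs are 4 weekly sessions and 15 minutes per session, both from Project Information item 9.

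Planned time in sessions with the dog = 4 × 15 = 60 minutes.

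This is time in the room with the dog. It is not 60 minutes of physical contact, because participants choose what to do and may simply sit with the dog. A student assigned to the education arm has no planned sessions with the dog.

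**The case against.** The strongest reply is that the decisive documents are not visible. The Qualtrics survey is only linked. The consent form is listed among the attachments but not shown, and the application form requires the listed risks to be described in it. Either may ask about or warn of reactions to dogs. Field 6.2 also asks for primary exclusions, so it need not be exhaustive. This stands as a limit: the gap is established for the criteria as written, not for the screen as it will operate. It does not remove the point, since a broader survey item would leave 6.2 out of step with it.

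Second, a student who knows they react to dogs would be volunteering knowingly. The team explains the study in person, consent is signed, and questions are invited throughout. That lowers the likelihood of the problem. None of these steps is described as an allergy check, though, and the protocol does not rely on self-selection to handle allergy.

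Third, *diagnosed* is a legitimate drafting choice that sets a clear threshold for self-report, and no passage contradicts it. That is fair. The point is that the threshold is poorly placed for its purpose, not that the protocol contradicts itself.

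A reader might go further and infer that such a participant would bias the comparison, because a reaction could alter heart rate or blood pressure after the session, or cause withdrawal, in the dog arm only. The protocol does not support this. The same criteria apply to all applicants, so eligibility does not differ by arm. Discomfort that the dog sessions cause in an eligible student is arguably part of the effect of those sessions. Nothing in the protocol says whether, or in which direction, a reaction moves these outcomes, and no withdrawal rate is given.

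A reader might also attach a size. Under an assumed equal split of the maximum 30 participants, each arm has 30/2 = 15, so one such student would be 1/15 = 6.7% of the dog arm and two would be 2/15 = 13.3%. The protocol gives no frequency of undiagnosed reactivity, and the number could be zero. These percentages restate an assumed count. They do not estimate risk or bias.

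**Conclusion.** The point holds as a matter of participant safety and eligibility wording. As written, 6.2 admits a student with a known but undiagnosed reaction to dogs, who may then be assigned to four 15-minute sessions with the dog, and the stated mitigations do not address allergy. The conclusion rests on a literal reading of 6.1, of 6.2 with its continuation, and of the risk section. It also assumes that the unseen survey and consent form do not already cover the case; if they do, what remains is to bring 6.2 into line with them. No statistical figure in the protocol changes, and neither a bias nor a numerical effect can be shown from it.

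**What to change.** Make three aligned changes.

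1. In 6.2, replace the allergy item with wording such as: *known or suspected dog allergy, including a self-reported reaction around dogs, whether or not diagnosed*.
2. Check the Qualtrics item and make it match. Screening at sign-up already applies to all applicants, so no change to the order of procedures is needed.
3. In Risks/Benefit Information item 2, name allergic reaction among the risks of dog contact, state in item 3 that the exclusion is how it is controlled, and confirm that the consent form says the same.

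The cost is one reworded criterion, one survey item and a sentence or two in the risk section and consent form. The downside is that a few more applicants may be screened out, including some whose reactions are trivial.
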